### **Data and Safety Monitoring Plan**

Study Monitoring: The proposed decolonization measures have been previously studied and pose minimal risk to study participants. Thus, a Data and Safety Monitoring Plan, rather than a formal Board, is appropriate. Monitors for this study include the PI ([name], MSCI), an independent monitor, [name], MSCR (Infectious Diseases specialist at Washington University), and the trial biostatistician, Professor [name]. The PI will monitor adverse events on a continuous basis and is responsible for providing the monitors with new safety information relevant to the study. The monitors will meet a minimum of twice per year and will review interim and cumulative data for evidence of study-related adverse events and for quality, completeness, and timeliness. The study monitors will assess compliance with study goals for patient recruitment and retention, protocol adherence, and factors external to the study that may impact patient safety or the ethics of the study. After each data evaluation, the monitors will consider continuation, modification, or termination of the trial. Ad hoc meetings may occur at the request of the monitors or the WU HRPO.

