## **METHODS**

Timeline: After randomization and distribution of study materials participants will have study visits every 3 months for 12 months to ascertain colonization status and development of subsequent SSTI.

Inclusion criteria: Households which participated in the "Community-Associated Methicillin-Resistant Staphylococcus aureus (CA-MRSA) Among Household Members and the Home Environment" study (HRPO 201104330). Only participants providing written, informed consent, or for whom consent is provided by a parent or legal guardian, will be included.

Exclusion Criteria: Households in which all members experienced SSTI during the 12-month natural history study will be ineligible to participate in the trial, to eliminate the bias that would be introduced if these families were randomized to the Individualized Approach arm. We will also not approach individuals who have declined contact for future studies on the HRPO 201104330 study consent form.

Procedures: The households participating in the "Community-Associated Methicillin-Resistant Staphylococcus aureus (CA-MRSA) Among Household Members and the Home Environment" (HRPO 201104330) study will be invited to enroll in this randomized trial upon completion of the 12-month follow-up period.

Randomization: Due to logistics and the use of objective outcome measures, this study will be performed as an open trial. Enrolled households will be allocated to one of two treatment groups (household vs. individualized decolonization) 1:1 randomization using the minimization method to assure balance in family size and composition (e.g., number of household members experiencing SSTI in the prior year). Minimization is a dynamic randomization algorithm that will help to ensure that treatment arms are balanced with respect to our predefined household factors as well as the number of households in each group. REDCap will be used to implement the minimization algorithm. Assignments will be generated by the REDCap program and revealed to the study coordinator immediately prior to the enrollment visit

Enrollment visit: Will take place in the participants' homes

- Time: 30-45 minutes
- The PI or research coordinator will provide standardized hygiene education curriculum regarding handling of lotions, soaps, hygiene items, and linens.
- Participants will be given instructions on how to perform the decolonization regimen (described below).

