### **INFORMED CONSENT**

Potential participants will be identified among participants in the "Community-Associated Methicillin-Resistant Staphylococcus aureus (CA-MRSA) Among Household Members and the Home Environment Study" (HRPO 201104330). The PI or research coordinator will provide verbal information and a letter explaining the study at the 9 month follow-up visit of the observational study. After household members have discussed the study amongst themselves, enrollment will take place at the 12 month follow-up visit of the observational study.

The enrollment visit will take place in the home. After the study design and expectations have again been described to all household members, the PI and study coordinator will obtain written informed consent from each household member. Parents or legal guardians will provide written consent for all minor participants. Children of a developmentally appropriate age (typically 7 years or older) will also be asked to sign an assent document.

Two different consent forms will be used: one for the individual approach group and one for the household approach group. Participants who agree to be in the study will be given the consent form for the treatment group to which they were randomized. The reason for having two consent forms is to minimize the chance that household members in the "Individualized Approach" arm who have not experienced SSTI in the prior 12 months (and thus NOT assigned to use the decolonization measures) will use the decolonization measures provided to the "affected" household members (those with SSTI in the prior 12 months).

The study team will emphasize that study participation is voluntary and the fact that if some household members do not wish to participate in the study, this does not exclude the remainder of the household from participation.

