#### Data to be reviewed:

1. Adverse Events
  - a. Description of individual serious and non-serious adverse events
  - b. Rates of serious and non-serious adverse events by study group, and overall
2. Patient Recruitment and Retention
  - a. Eligibility and refusal rates for subjects
  - b. Reasons for exclusion

- c. Baseline demographic characteristics of randomized participants and household characteristics to check adequacy of randomization (including gender, race/ethnicity, number of household members overall, and number of individuals per household experiencing SSTI during the natural history study)
- d. Attrition rates by study group (only available during the follow-up period)

3. Outcomes
  - a. Incidence of SSTI (Primary outcome is SSTI incidence 3 months following decolonization)
  - b. MRSA colonization status of study participants
4. Protocol Violations
  - a. Descriptions of any protocol violations that occur

Stopping Criteria: Interim analysis for the primary outcome, incidence of SSTI 3 months following decolonization, will be conducted approximately every 6 months throughout the trial (~4 times). The trial will be terminated or modified upon interim data analysis if there is overwhelming evidence of the benefit of one treatment arm compared to the other arm of the study, defined as an absolute difference of 50% in the 3-month incidence of SSTI during the longitudinal study period between the Individualized Approach and Household Approach arms. The Lan-DeMets spending function approach will be used to examine our primary outcome when interim analyses are performed to allow for flexible interim monitoring while also preserving the type-I error of the study.

Reporting: A safety and interim analysis report will be generated by the monitors twice annually. As required by the WU HRPO, the PI will report the following serious adverse events to the WU HRPO using methods specified by the WU HRPO: deaths will be reported immediately, life-threatening events will be reported within 7 calendar days, and all other serious adverse events will be reported within 15 calendar days.

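### The PI, who takes consent with the arm known in an open trial, is also one of the three monitors, and nothing shields the PI from interim SSTI results by arm

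*Combined protocol and SAP*

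**What the plan says.** All references are to the combined protocol and SAP.

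- **Monitoring.** Under Data and Safety Monitoring Plan, Study Monitoring: "Monitors for this study include the PI", together with one independent monitor and the trial biostatistician. There is no formal board. The monitors weigh whether the trial goes on, changes or stops.
- **Data seen.** Under Data to be reviewed, the list includes SSTI incidence (named there as the primary outcome) and MRSA colonization. Under Reporting: "A safety and interim analysis report will be generated by the monitors twice annually".
- **Interim looks.** Under Stopping Criteria, the primary outcome is analysed about every 6 months, roughly four times, against a 50-point difference between the arms.
- **Blinding.** Methods, Randomization: "Due to logistics and the use of objective outcome measures", "this study will be performed as an open trial".
- **Consent.** Informed Consent: "the PI and study coordinator will obtain written informed consent from each household member". Also: "Participants who agree to be in the study will be given the consent form for the treatment group to which they were randomized".
- **Education.** Methods, Enrollment visit: "The PI or research coordinator will provide standardized hygiene education curriculum".
- **Outcome.** Participants report infections by survey at the follow-up visits. If they sought medical care, the study team gathers and checks the details.

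**The concern.** Someone who has seen which arm is ahead may, without meaning to, act differently in the parts of the trial that depend on judgement. Those parts are how consent is discussed with individual household members, how education and adherence support are given, and how hard records are chased when an infection is reported. Blinding is absent here, so the main protection left is to keep the compiled comparison away from people who run the trial. The plan does the opposite for the PI, by making the PI a member of the group that reviews it.

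The issue carries weight because the conclusion turns on whether the upper confidence limit for the arm difference lies below 10 points. Uneven conduct or ascertainment between arms would act directly on that difference.

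**Working it through.** The point depends on how the sections fit together and not on a planned figure, so the check sets them side by side.

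1. **Does the PI belong to the group that sees interim outcomes?** Yes, as stated. The PI is one of three monitors, SSTI incidence and colonization are on the monitors' list, and the monitors write the interim report.

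2. **Do the monitors see SSTI by arm?** This is implied, not stated. In Data to be reviewed, adverse-event rates and attrition are marked as being by study group; SSTI and colonization are not. But the stopping criterion is a difference of 50 points between arms. With the planned 9% in the Household arm (Statistical Plan), that means for example 9% against 9 + 50 = 59%. Such a rule cannot be applied to pooled data. The text does not say who runs the comparison.

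3. **What does the PI do in the trial?**
   - Consent: stated, with the study coordinator, on a form specific to the arm, so the arm is known.
   - Education: the PI or the research coordinator, so the PI may deliver it.
   - Follow-up visits: no person is named.
   - Verification of infections: the study team, which the PI leads. A personal part for the PI is an inference.

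4. **Do the looks overlap with trial conduct?** Probably. Households are invited as each completes the 12-month parent study, so entry is staggered. Four looks at 6-month intervals span about 4 x 6 = 24 months. If all households had entered together, the 3-month outcome would be complete before the first 6-month look and later looks would add nothing. Repeated looks therefore make sense only while households are still entering or reaching 3 months. Each household's own 12-month follow-up spans about 12 / 6 = 2 looks.

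5. **Which steps leave room for judgement?** Individual members may decline without excluding the household (Informed Consent), and the primary outcome covers all participants (Statistical Plan). A telephone call at 7 to 10 days checks completion of the regimen. Verification of infections extends to whatever detail the team can obtain, and no blinded assessor is named.

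6. **Is there a safeguard?** None was found: no closed session, no pooled-only report for the PI, no blinded outcome assessment. The confidentiality section limits data-entry device access to the study team but describes no restriction within the team.

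Steps 1, 3 (consent) and 6 rest on the text. Steps 2 and 4, and the PI's personal part in education and outcome collection, are inferences.

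**The case against.** Several counterarguments have force.

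- **Enrolment is constrained.** Households come from a closed cohort, REDCap minimization makes the allocation, and it is revealed to the coordinator just before the visit. This limits discretion over which households enter. It does not cover individual members' consent once the arm is known.
- **Capture and education are structured.** Participants complete surveys at fixed visits and the curriculum is standardized. That limits influence on first reporting and on the content of the education, but less so on verification and adherence support. The plan's appeal to objective outcomes therefore mitigates only in part, since SSTI is first self-reported.
- **Oversight is proportionate.** The plan gives minimal risk as its reason for having no board, and it names an independent monitor. That justifies the absence of a board but does not explain why the PI should see outcomes by arm.
- **A firewall would be incomplete.** At a single site the PI knows assignments from the consent forms and leads the team that hears of infections, so a tally by arm could be made without any report. This stands, and it is why the fix must also bar the PI and field team from producing such summaries.

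A reader might infer that the PI personally collects outcomes, or that the plan states the PI will receive by-arm SSTI. Neither is in the text. A reader might also infer that the bias would favour non-inferiority, because the plan hypothesizes equal effectiveness. A narrowed difference would do so, but nothing in the documents shows that the PI's knowledge would narrow the difference rather than widen it.

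**Conclusion.** The concern holds as a risk in the design, not as an error or a demonstrated bias. The PI's place among the monitors, the PI's part in consent with the arm known, and the lack of any shield are stated or directly checkable. By-arm access is a strong inference from the stopping criterion. If pooled review was intended, the same edit would settle it.

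The size and direction of any bias cannot be derived. A reader might be tempted to attach a figure. As a purely hypothetical example, suppose true rates of 9% and 19% with 3 points of the difference hidden, so that 9% and 16% are observed:

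- SE = sqrt[1.4 x (0.09 x 0.91 + 0.16 x 0.84) / 172] = 0.04196, or 4.196 points.
- Chance of falsely declaring non-inferiority = Phi((10 - 7) / 4.196 - 1.96) = Phi(-1.245) = 0.107, against a nominal 0.025.

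The 3 points are chosen, not derived. They would require about 0.03 x 172 = 5 of about 0.19 x 172 = 33 events to be lost, in one arm only. No section links such a loss to the PI seeing summaries, and the same sum would illustrate uneven ascertainment in any open trial. The figure therefore carries no weight here. The case for change is that the risk is recognised, avoidable and cheap to reduce.

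**What to change.** In the Data and Safety Monitoring Plan (Study Monitoring, Data to be reviewed, Stopping Criteria and Reporting), state that:

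1. Interim SSTI and colonization results by arm are compiled by the trial biostatistician and seen only by the biostatistician and the independent monitor, who also write that part of the interim report.
2. The PI and field team do not produce or receive by-arm outcome summaries before the final analysis.
3. The PI receives pooled outcome data, individual adverse-event reports and the monitors' recommendation.

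**Cost.** This is mainly protocol wording, and both people are already named. Item 2 needs a working limit on who can compile or export by-arm outcome data, which the data-security section does not now describe. The PI loses the by-arm interim view, and by-arm review rests on two people, one of whom the plan does not call independent. The PI's continuous adverse-event monitoring and reporting to the HRPO are unchanged. The PI can still learn individual outcomes with the arm known, so the change reduces the risk without removing it. It also leaves the lack of blinded verification of self-reported infections as it is.

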#### Data to be reviewed:

1. Adverse Events
  - a. Description of individual serious and non-serious adverse events
  - b. Rates of serious and non-serious adverse events by study group, and overall
2. Patient Recruitment and Retention
  - a. Eligibility and refusal rates for subjects
  - b. Reasons for exclusion

- c. Baseline demographic characteristics of randomized participants and household characteristics to check adequacy of randomization (including gender, race/ethnicity, number of household members overall, and number of individuals per household experiencing SSTI during the natural history study)
- d. Attrition rates by study group (only available during the follow-up period)

3. Outcomes
  - a. Incidence of SSTI (Primary outcome is SSTI incidence 3 months following decolonization)
  - b. MRSA colonization status of study participants
4. Protocol Violations
  - a. Descriptions of any protocol violations that occur

Stopping Criteria: Interim analysis for the primary outcome, incidence of SSTI 3 months following decolonization, will be conducted approximately every 6 months throughout the trial (~4 times). The trial will be terminated or modified upon interim data analysis if there is overwhelming evidence of the benefit of one treatment arm compared to the other arm of the study, defined as an absolute difference of 50% in the 3-month incidence of SSTI during the longitudinal study period between the Individualized Approach and Household Approach arms. The Lan-DeMets spending function approach will be used to examine our primary outcome when interim analyses are performed to allow for flexible interim monitoring while also preserving the type-I error of the study.

Reporting: A safety and interim analysis report will be generated by the monitors twice annually. As required by the WU HRPO, the PI will report the following serious adverse events to the WU HRPO using methods specified by the WU HRPO: deaths will be reported immediately, life-threatening events will be reported within 7 calendar days, and all other serious adverse events will be reported within 15 calendar days.
